2.2 Study Objectives

1a. To measure the proportion of participants with an Irregular Rhythm Notification (IRN) prior to enrollment who have atrial fibrillation or atrial flutter (AF) confirmed by ambulatory electrocardiographic (ECG) patch monitoring.

1b. To measure the proportion of participants with an ECG app classification of Atrial Fibrillation (ECG app-AFib) prior to enrollment who have AF confirmed by ambulatory ECG patch monitoring.

2a. To measure the proportion of participants who receive an IRN or ECG app-AFib reporting contact with a non-study healthcare provider at 15 and 60 days after study enrollment.

2b. To measure the proportion of participants with an ECG app classification of inconclusive prior to enrollment who have AF confirmed by ambulatory ECG patch monitoring.

2c. To measure the proportion of participants who have AF confirmed by ambulatory ECG patch monitoring by age at enrollment (< 65 and 65+).

This document contains information that is privileged or confidential and may not be disclosed unless such disclosure is required by applicable laws and regulations. The information in this document is the property of Apple Inc. and may not be reproduced, published, or disclosed to others without written authorization from Apple Inc.

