5.0 STUDY POPULATION

5.1 Inclusion Criteria

1. Possession of the following at time of eligibility screening, ascertained from automatic hardware/software/device pairing check:
 - I. iPhone (5s or later) with iOS version 12.1.1 or later defined as iPhone model/iOS version used to complete screening eligibility.
 - II. Apple Watch (Series 1-4) with watchOS version 5.1.2 or later defined as Apple Watch model/watchOS paired with iPhone used to complete screening eligibility.
2. At least one of the following by self-report before consent:
 - I. Irregular Rhythm Notification
 - II. ECG app classification of Atrial Fibrillation
 - III. ECG app classification of Inconclusive defined as “Inconclusive,” “Heart Rate Over 120,” or “Heart Rate Under 50”
3. Age \geq 22 years at time of eligibility screening, ascertained from self-reported date of birth.
4. Current resident of the United States at time of eligibility screening, defined by self-reported state of residence within the 50 states of the United States or District of Columbia, and will reside in the United States for the length of the study.
5. Proficient in written and spoken English, defined by self-report of comfort reading, writing, and speaking English on iPhone.
6. Valid phone number associated with iPhone, ascertained from self-report.
7. Valid email address, ascertained from self-report.

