10.5 Sample Size and Power Considerations

This clinical study is not designed to test any pre-specified statistical hypotheses. Because all participants enrolling in this clinical trial will either have received an irregular rhythm notification (IRN) or an ECG app-AFib classification, this sample size justification applies to Objectives 1a and 1b. To address our aims, we require 400 IRN participants that are exclusively in the IRN group (i.e., who do not enter the study via the ECG app), who are deemed eligible for ePatch receipt and who return their ePatches, and 400 participants who exclusively enroll via the ECG-app classification of AFib, who are deemed eligible for ePatch receipt and who return their ePatches. This sample size provides sufficient precision for our purposes, yielding a 95% confidence interval with a width that is no greater than 0.10 when addressing the primary objectives. Further, it does not require assessment or unblinding of ePatch results on an ongoing basis. If, after enrolling 500 participants, we observe that there is 50% overlap or greater between participants who enroll through both the IRN and the ECG app, we will modify our targeted enrollment with the understanding that the reporting of findings will be accompanied with a detailed context of the types of subjects that contribute to both the point estimates of interest. Given these considerations, a targeted enrollment of 2600 participants is suggested. This allows for approximately a 35% attrition rate and a 50% overlap between participant types (IRN vs ECG-app).

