The ECG app is a software-only mobile medical application intended for use with the Apple Watch to create, record, store, transfer, and display a single channel ECG similar to a Lead I ECG. The ECG app processes electrical signals from two sensors on the Apple Watch - an electrode on the back of Apple Watch and an electrode on the digital crown. A user opens the ECG app on their Apple Watch, places a finger on the digital crown, and remains still for 30 seconds to capture an ECG. The ECG app analyzes the waveform to determine the presence of atrial fibrillation (AF) or sinus rhythm on a classifiable waveform. The ECG app waveform is stored in the Health App and can be exported as a .pdf. The ECG app provides rhythm classifications such as AF, “Inconclusive”, “Heart Rate Over 120”, or “Heart Rate Under 50”. The ECG app group classifications; “Inconclusive”, “Heart Rate Over 120”, or “Heart Rate Under 50” are all considered inconclusive for the purposes of this study and are considered eligible for this study. Both the IRN feature and the ECG app were granted United States Food and Drug Administration (FDA) de novo classification on 9/11/2018.

Participants who call into AppleCare and self-report having received an IRN or ECG app classification of AF or inconclusive will be offered information about participation in the study. The AppleCare representative will offer to e-mail the participant a link to download the Study App for more information. If the participant agrees, the participant will be emailed a link to download the Study App. Once downloaded, the Study App will provide the information about the study and screen for eligibility. If the participant meets the eligibility criteria and wishes to enroll in the study, the Study App will initiate the consenting process and provide the consent and authorization to sign in the app. Participants who install the Apple Heart Study 1.2 App and meet the eligibility criteria proceed to consent and then enroll in the study. Participants will be required to provide signed informed consent; once enrolled they will complete a short questionnaire to collect demographic information, medical history, and health status, after which the study period will commence.

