1.3 Number of Participants Needed to Address Objectives

This clinical study is not designed to test any pre-specified statistical hypotheses. Because all participants enrolling in this clinical trial will either have received an IRN or an ECG app-AFib classification, we derived the number of enrolled participants needed to achieve our desired precision for addressing Objectives 1a and 1b.

To obtain a 95% confidence interval (CI) with a width no greater than 0.10 when addressing Objective 1a we will require 400 IRN participants that are exclusively in the IRN group (i.e., who do not enter the study via the ECG app), who are deemed eligible for ePatch receipt and who return their ePatches. Similarly, for Objective 1b to obtain a 95% CI with a width no greater than 0.10 we will require 400 participants who exclusively enroll via the ECG-app classification of AFib, who are deemed eligible for ePatch receipt and who return their ePatches.

The figure above displays the 95% CI width for the target sample size of 400 (over the range of possible AF percents we could observe) and three sample sizes that represent a failure to meet the target; n=350 (87.5% of target), n=300 (75% of target) and n=200 (50% of target). The height of the lines (the vertical axis) correspond to the CI width. The horizontal axis corresponds to the percent AF observed. As noted 400 patches (the blue line) will ensure the estimated CIs are no wider than 10%. The lines representing a failure to meet the target number of returned ePatches for each group shows at worst the CI could be as wide as 13.9% at 50% of the target and a percent with AF of 50%. However, even at 87.5% or even 75% of the recruitment target the worst case is a CI width of 11.3% and in both cases a modest amount of possible AF percentages will yield a CI with a width < 10%.

If, after enrolling 500 participants, we observe that there is 50% overlap or greater between participants who enroll through both the IRN and the ECG app, we will modify our targeted enrollment with the understanding that the reporting of findings will be accompanied with a detailed context of the types of subjects that contribute to both estimates addressing Objectives 1a and 1b.

Allowing for an approximate attrition rate of 35% and an overlap of 50% between participant types (IRN vs ECG-app) we calculated a minimum target enrollment of 2600 participants.

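### The sizing assumes every enrollee has an IRN or ECG app-AFib result, but Inconclusive alone qualifies, so 2600 is not shown to yield 400 + 400 exclusive patches (minor)

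*Combined protocol and SAP*

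**What the plan says.** Protocol 10.5 opens its sizing argument with "Because all participants enrolling in this clinical trial will either have received an irregular rhythm notification (IRN) or an ECG app-AFib classification". SAP 1.3 repeats it, "Because all participants enrolling in this clinical trial will either have received an IRN or an ECG app-AFib classification", and gives it as the reason for the enrolment number it derives for Objectives 1a and 1b.

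Both sections require 400 returned ePatches from people who are exclusively IRN and 400 from people who are exclusively ECG app-AFib, so that a 95% interval is no wider than 0.10. On the step from patches to enrollees, protocol 10.5 says: "This allows for approximately a 35% attrition rate and a 50% overlap between participant types (IRN vs ECG-app". SAP 1.3 cites the same two allowances and concludes: "we calculated a minimum target enrollment of 2600 participants".

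The eligibility text is broader. Protocol 5.1, criterion 2, asks for "At least one of the following by self-report before consent", and its third item is "ECG app classification of Inconclusive defined as" any of three app outputs. SAP 1.2 says of those outputs that they "are all considered inconclusive for the purposes of this study and are considered eligible for this study". Protocol 10.1 lists Inconclusive as one of three enrolment cohorts. Objective 2b is "To measure the proportion of participants with an ECG app classification of inconclusive prior to enrollment who have AF confirmed" on the patch. Protocol 10.6 describes the population as enriched for inconclusive results.

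**The concern.** The premise is false under the plan's own eligibility rule. Someone whose only qualifying result is Inconclusive takes one of the 2600 places but cannot belong to either exclusive group of 400. Neither section gives the expected share of such people or makes an allowance for them.

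The term 50% overlap adds to the difficulty. It may mean half of all enrollees or half of each group. The shorthand IRN versus ECG-app also leaves open whether an Inconclusive result counts on the ECG-app side. At stake is whether 2600 can be shown to produce the exclusive groups that the plan says it needs.

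**Working it through.** **Inputs from the documents:** 400 + 400 exclusive returned patches; attrition about 35%; overlap 50%; enrolment 2600 (protocol 10.5, SAP 1.3).

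**Assumptions:** the Inconclusive-only share f is not given, so 0%, 10% and 20% are used as illustrations. The IRN and ECG app-AFib groups are taken as equal. Attrition is taken as the same in all cohorts.

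**1. The plan's own figures.** The Gaussian width at p = 0.5 is 2 × 1.96 × √(0.25/n). This gives 0.098 at n = 400, 0.113 at n = 300 and 0.139 at n = 200. The last two match the 11.3% and 13.9% in SAP 1.3, so the precision figures reproduce.

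The enrolment figure does not reproduce exactly. No formula is given. With overlap as half of all enrollees, 800 / (0.65 × 0.50) = 2462. With overlap as half of each group, the exclusive IRN, overlap and exclusive AFib blocks are equal, so 3 × 400 / 0.65 = 1846. I therefore take 2600 as given and run it forward.

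**2. Exclusive yield of 2600.** Returned patches: 2600 × 0.65 = 1690.

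| Meaning of 50% overlap | Inconclusive-only people | Exclusive yield | f at which 400 + 400 is missed |
|---|---|---|---|
| Half of all enrollees | outside the split | 845 × (1 − f) in total | 1 − 800/845 = 5.3% (about 138 of 2600) |
| Half of each group | outside the split | 563.3 × (1 − f) per group | 1 − 400/563.3 = 29.0% |
| Half of all enrollees | on the ECG-app side | AFib-only: 422.5 − 1690f | 22.5/1690 = 1.3% |
| Half of each group | on the ECG-app side | AFib-only: 563.3 − 1690f | 163.3/1690 = 9.7% |

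Here 845 = 1690 × 0.50, 422.5 = 845/2 and 563.3 = 1690/3. At f = 0%, 10% and 20% the first row gives 845, 760 and 676 in total. The second gives 563, 507 and 451 per group.

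**3. Sensitivity of the first row.**
- Attrition of 33% gives 2600 × 0.67 × 0.50 = 871 and a threshold of 1 − 800/871 = 8.2%.
- Attrition of 37% gives 819 and 1 − 800/819 = 2.3%.
- With unequal groups and f = 0, one group is already short if it holds under 400/845 = 47.3% of the exclusive patches.

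**4. What Objectives 1a and 1b actually use.** Protocol 10.3.1 and SAP 4.3 divide by everyone in the EAS who had the relevant notification before enrolment, not by the exclusive group. Assume that overlap participants hold both an IRN and ECG app-AFib. At f = 20%, 1690 × 0.80 = 1352 patches come from people with at least one of the two. Each denominator is then:
- overlap as half of all: 338 exclusive + 676 overlap = 1014;
- overlap as half of each group: 1352/1.5 = 901;
- no overlap at all: 1352/2 = 676.

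The worst-case Gaussian width at 676 is 1.96/√676 = 0.075. The denominators fall to 400 only when f reaches 1 − 400/1267.5 = 68.4%, 1 − 400/1126.7 = 64.5% or 1 − 400/845 = 52.7% respectively.

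These counts are returned patches. The EAS (protocol 10.1) also requires one hour of usable data and no fallout, so realised numbers may be somewhat lower.

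**The case against.** The strongest reply is that nothing the study reports depends on the exclusive count. The 400s serve a width of 0.10 for 1a and 1b, and those analyses use larger denominators. This stands, and it is the main reason why the point is minor.

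Three further replies also have force:
- SAP 1.3 already shows the worst-case widths if the exclusive target is missed, and treats a shortfall as tolerable. The 380 and 338 per group implied by f = 10% and 20% in the first row lie within the 200 to 400 that it covers.
- 2600 is called a minimum. Protocol 7.1 and SAP 5 review enrolment by cohort at day 60, and recruitment can then be redirected or extended.
- Overlap is not wholly undefined. Both sections describe an exclusive IRN participant as one who did not come in through the ECG app, which suggests that IRN plus Inconclusive is not exclusive IRN. The base of the 50% is still not given.

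The premise might be defended as a loose statement of scope, meaning only that the sizing concerns 1a and 1b. That does not stand: SAP 1.3 makes it the reason for the derivation. The safeguards also leave the gap in place. The check after 500 enrollees looks at overlap, not at the Inconclusive-only share, and the day-60 review measures progress toward a target whose basis is misdescribed.

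**Conclusion.** Wrong as written, and minor. Protocol 10.5 and SAP 1.3 misstate who can enrol and make no allowance for Inconclusive-only participants. They therefore do not show that 2600 yields 400 + 400 exclusive patches. The share at which that count is missed, in expectation, is about 5.3% or 29% according to what 50% overlap means, and about 1.3% or 9.7% if Inconclusive-only people sit on the ECG-app side. All four figures assume 35% attrition and equal groups. Because f is not given, an actual shortfall is neither shown nor excluded.

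A reader might infer that 1a or 1b will miss the 0.10 width, or that enrolment must rise (on the first reading at f = 20%, 800 / (0.325 × 0.80) = 3077 would keep 800 exclusive patches). The documents support neither inference. At that share the denominators are about 676 to 1014, and they stay above 400 until f passes roughly 53% to 68%. This rests on the equal split and on overlap participants holding ECG app-AFib as well as an IRN. An unequal split, or overlap made up largely of IRN plus Inconclusive, would reduce the 1b denominator; the documents give no figures for either.

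**What to change.** In both protocol 10.5 and SAP 1.3:

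1. Replace the premise with wording such as: *Participants may enroll on an IRN, an ECG app-AFib or an ECG app-Inconclusive result. This sizing applies to Objectives 1a and 1b. Participants whose only qualifying result is Inconclusive count toward 2600 but toward neither group of 400.*
2. Define 50% overlap as a share of all enrollees or of each group, consistently with the existing statement that exclusive IRN means not entering through the ECG app. Apply the same definition to the check after 500 enrollees.
3. State an assumed f with a range, and the exclusive yield of 2600 under it. For example, at 0%, 10% and 20%, give 845, 760 and 676 in total if overlap is half of all, or 563, 507 and 451 per group if it is half of each, with the assumed split.
4. Reword the 400 + 400 requirement as a target for exclusive patches, so that it does not sit beside yields below 800. Say that the 0.10 width for 1a and 1b rests on their full denominators, exclusive plus overlap participants.

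Which interval applies is a separate matter: protocol 10.3.1 and SAP 4.3 specify an exact interval, and SAP 4.1 a Gaussian one. It should be settled there.

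The cost is a few sentences in two sections, with no extra enrolment and no change to any analysis. The downside is a less favourable stated yield for the exclusive groups.

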10.6 Limitations

Because the study population is enriched for participants with irregular rhythms and inconclusive results who call AppleCare in response to receiving an IRN, an ECG classification of Atrial Fibrillation, or an ECG classification of Inconclusive, the results of this study may not be generalizable to the broader population of Apple Watch users.

This document contains information that is privileged or confidential and may not be disclosed unless such disclosure is required by applicable laws and regulations. The information in this document is the property of Apple Inc. and may not be reproduced, published, or disclosed to others without written authorization from Apple Inc.

11.1 TRAINING

To ensure accurate, complete, and reliable data, the Stanford study team in conjunction with sponsor, will provide instructional material to Study Telehealth Provider, BioTelemetry, ECG Adjudicating Clinicians and other study personnel as appropriate.

12.0 ETHICAL AND REGULATORY CONSIDERATIONS

This study will be conducted in accordance with applicable FDA regulations (21 CFR Parts 11, 50, 54, 56, 803, and 820, as applicable).

12.1 Institutional Review Board

The protocol must be submitted to the appropriate Institutional Review Board (IRB) and written approval must be obtained prior to enrolling any participants. Yearly approvals for the continuation of the study must be obtained by the Investigator.

In addition to the IRB reports submitted during the yearly approval process, certain events require prompt reporting to the IRB. The timeline and type of events will follow the most updated policy of the governing IRB, but in general, those events, as relevant to this protocol, include:

1. Unanticipated Problems Involving Risks to Participants or Others (UPs): Events (internal or external, deaths, life-threatening experiences, injuries, or other) occurring during the research study, which meet all of the following criteria:
 - a. Unexpected in terms of nature, severity, or frequency; and
 - b. Related to participation in the research or there is a reasonable possibility or likelihood that the event may have been caused by the procedures involved in the research; and
 - c. Harmful – places research participants or others at a greater risk of harm than was previously known or recognized.
2. New Information that indicates a change to the risks or potential benefit of the research in terms or severity or frequency or impacts the participant's willingness to participate.
3. Noncompliance with the IRB approved protocol and other applicable policies when the event is:
 - a. Possibly serious (affects the rights and welfare of participants)
 - b. Possibly continuing (a pattern of noncompliance that continues to occur)
4. Complaint that is unresolved by the research team
5. Other events or information

This document contains information that is privileged or confidential and may not be disclosed unless such disclosure is required by applicable laws and regulations. The information in this document is the property of Apple Inc. and may not be reproduced, published, or disclosed to others without written authorization from Apple Inc.

12.2 Informed Consent and HIPAA Authorization

The Informed Consent will be provided within the study app and will employ ResearchKit electronic consent framework for the signature view to obtain signed and dated informed consent and HIPAA authorization prior to enrollment. Signed consent forms will be stored on an encrypted server which is 21 CFR Part 11 compliant. The protocol and informed consent form must be approved by the reviewing IRB prior to commencement of the study. Any subsequent revisions to the informed consent form must also receive IRB approval prior to use.

12.3 Confidentiality of Participants

Participant confidentiality will be maintained throughout the clinical study in a way that ensures the information can always be tracked back to the source data. For this purpose, a unique participant identification code (ID number) will be used that allows identification of all data reported for each participant. The ID number will be randomly generated.

Participant information collected in this study will comply with the applicable standards for protection of privacy of individually identifiable health information. The Sponsor, investigators and all study affiliates will make every reasonable effort to protect the confidentiality of the participants participating in this study. Participant records may be released to governing regulatory authorities, if requested. In all cases, caution will be exercised to assure the data are treated confidentially and that the participant's privacy is protected.

13.0 HUMAN SUBJECTS PROTECTION

13.1 Research participant Selection and Justification of Exclusions

There will be no exclusion from participation in the study on the basis of ethnicity or race. Participants younger than 22 years of age will be excluded from the study, as the target population is adults \geq 22 years. Participants who are not proficient in written English will be excluded as this will prohibit informed consent as well as completion of any necessary data collection forms. Participants with shared iCloud accounts or Apple Watches will be excluded due to inability to confirm participant-level measures and outcomes.

13.2 Compensation to participants

There will be no direct monetary remuneration to study participants.

This document contains information that is privileged or confidential and may not be disclosed unless such disclosure is required by applicable laws and regulations. The information in this document is the property of Apple Inc. and may not be reproduced, published, or disclosed to others without written authorization from Apple Inc.

